#### Pharmacovigilance.

The study will be paused to assess the safety of study continuation using the following SRs that will be applied to all study subjects throughout the trial:

- 1. An SAE that is determined to be possibly, probably, or definitely related to the study product;
- 2. An AE related to the study product that the PI, RM, and/or the sponsor's PVG MD agree jeopardizes the subject's health or safety;
- 3. An AE related to the study product that requires medical or surgical intervention to prevent occurrence of an SAE;
  - 4. A post-infusion, coagulation function assay result that is abnormal and also greater than a 20% change from the baseline value recorded for prothrombin time and international normalized ratio (PT/INR) and/or activated partial thromboplastin time (aPTT) (eg, a subject who has a baseline INR of 1.0 with a post-infusion INR of 1.3 will activate an SR, because this is an abnormal coagulation function assay result that is also a greater than 20% change from the pre-infusion assay result); and/or
- 5. Post-infusion development of deep vein thrombosis (DVT), cardiac ischemia, pulmonary embolism (PE), or hemolysis.

Data and Safety Monitoring Board (DSMB). A designated DSMB will formally review subjects' data following the completion of infusions in each cohort for the purpose of assessing safety. DSMB meetings will be scheduled to maximize the amount of subject data reported to the DSMB through the 28-day follow-up visit. The DSMB will have at a minimum all data through the 7-Day Follow Up Visit. Following each meeting, the DSMB will provide the sponsor with a recommendation about proceeding with infusions in the subsequent cohort. Following the meeting to review Cohort 3 data, the DSMB will provide a recommendation about proceeding with the next planned FDP trial. After the receipt and consideration of each DSMB recommendation, the sponsor will make a final determination about proceeding to the next cohort or the next FDP trial.

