# 6.9. Dose-Adjustment Criteria

## 6.9.1. Safety Criteria for Dose Adjustment or Stopping Doses

If any of the following events occur, administration of investigational product will be discontinued until a thorough review of the events is undertaken by the PI, local Institutional Review Board (IRB) and/or the USAMRMC Office of Research Protections (ORP) Human Research Protection Office (HRPO), RM, and/or sponsor's safety office (USAMMDA, ORA, PSSB). The study may be resumed with the concurrence of the PVG MD, sponsor's representative, PI, and the FDA.

The following SRs will be applied to all study subjects throughout the trial:

- 1. An SAE that is determined to be possibly, probably, or definitely related to the study product;
- 2. An AE related to the study product that the PI, RM, and/or the sponsor's PVG MD agree jeopardizes the subject's health or safety;
- 3. An AE related to the study product that requires medical or surgical intervention to prevent occurrence of an SAE;
- 4. A post-infusion, abnormal coagulation function assay which is also a greater than 20% change from baseline for PT/INR and/or aPTT values (eg, a subject who has a baseline INR of 1.0 with a post-infusion INR of 1.3 will activate an SR, because this is an abnormal coagulation function assay result that is also a greater than 20% change from the pre-infusion assay result); and/or
- 5. Post-infusion development of hemolysis or DVT, cardiac ischemia, or PE. DVT will be determined following the ICSI Health Care Guideline: Venous Thromboembolism Diagnosis and Treatment (includes assessment of D-Dimer results and Wells criteria ≥ 2). (Dupras et al-2013)

If any of the above conditions occur, the study will be paused to assess continuation of the study. A form (Appendix C) will document the decisions made by the PI, RM, and/or PVG MD regarding the review of the data from the first 5 subjects in each cohort. The completed form will be emailed to the clinical site, Westat, and USAMRMC USAMMDA ORA and will be maintained as part of the study documentation.

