### 10.2.1. Adverse Event or Suspected Adverse Reaction

An AE is defined as any untoward medical occurrence associated with the use of a drug/biologic in humans, whether or not it is considered to be related to the drug/biologic.

A suspected AR is any AE for which there is a reasonable possibility that the drug/biologic caused the AE. For the purposes of IND safety reporting, a "reasonable possibility" means there is evidence to suggest a causal relationship between the drug/biologic and the AE. Suspected AR implies a lesser degree of certainty about causality than AR, which means any AE caused by a drug/biologic.

An AE or suspected AR is considered "life-threatening" if, in the view of either the investigator or sponsor, its occurrence places the patient or subject at immediate risk of death. It does not include an AE or suspected AR that, had it occurred in a more severe form, might have caused death.

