# 10.3. Relationship to Investigational Product

The site PI must assign a relationship of each AE to the receipt of the investigational product. The PI will use clinical judgment in conjunction with the assessment of a plausible biologic mechanism, a temporal relationship between the onset of the event in relation to receipt of the investigational product, and identification of possible alternate etiologies including underlying disease, concurrent illness, or concomitant medications. The following guidelines should be used to assess the relationship of an AE to study product administration and **ONLY A PHYSICIAN CAN MAKE THIS DETERMINATION:** 

**Not related:** There is no reasonable causal relationship between the investigational product administered and the SAE. Applies to those events for which an alternate etiology exists.

**Unlikely:** Likely unrelated to the investigational product. Likely to be related to factors other than investigational product, but cannot be ruled out with certainty.

**Possible:** An association between the event and the administration of investigational product cannot be ruled out. There is a reasonable temporal association, but there may also be an alternative etiology such as the subject's clinical status or underlying factors including other therapy.

**Probable:** There is a high degree of certainty that a relationship to the investigational product exists. There is a reasonable temporal association, and the event cannot be explained by known characteristics of the subject's clinical state or factors including other therapy.

**Definite:** An association exists between the receipt of an investigational product and the event. An association to other factors has been ruled out.

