## 11.1.3. Safety Analyses

AEs will be coded using the most recent version of the Medical Dictionary of Regulatory Activities preferred terms and will be grouped by system, organ, class designation (SOC).

AEs will be summarized using standard FDA-recommended templates distinguishing those defined as TEAEs. A TEAE will be defined as an AE that emerges during or following treatment (infusion), having been absent pretreatment. For all TEAEs, relatedness to infused product will be presented. TEAEs related to study treatment will be defined as definitely or probably related to study treatment.

Use of the Centers for Disease Control National Healthcare Safety Network Hemovigilance Module criteria will ensure consistent definitions are applied when using transfusion-related event terms, such as transfusion related acute lung injury or transfusion associated circulatory overload. The National Cancer Institute Common Terminology Criteria will be used to assess all AEs for toxicity grade, or severity, regardless of whether the event is transfusion-related (HHS-2010). AEs will also be presented by maximum severity or maximum common terminology criteria for AE (CTCAE) grade (depending on collection). A summary of SAEs and a summary of AEs leading to treatment discontinuation will be presented.

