Special Note: For Cohort 3, there will be an Open and Closed session for the DSMB. For the Open session only Figure 2 will only show overall totals as shown above with the figure number having the word “(Open)” after the figure number before the decimal. Open session Figure 2 will be produced by the blinded statistician. For the Closed session, the treatment arms will be masked as A and B as shown above. The figure number will have the word “(Closed)” after the figure number before the decimal. Closed session Figure 2 will be produced by the unblinded statistician. Final data analysis for Cohort 3 will use the labels FDP-ACDxFFP and FFPxFDP-ACD for the treatments after the study is unblinded and the word “(Closed)” will be removed from the figure number.

Table 2.1. - Table 2.15. Overview of Subject Incidence of Adverse Events (AEs)

Subject Incidence of AEs – Cohort 1 (270 mL)

Full Analysis Population – F1 (N=XX)

**FDP-1
 Phase I**

	FDP-CPD (N=XX) n (% ^a)	FDP-ACD (N=XX) n (% ^a)
Adverse Events	xx (xx.x)	xx (xx.x)
Treatment Emergent Adverse Events	xx (xx.x)	xx (xx.x)
Treatment-Emergent Adverse Events Related to Study Treatment	xx (xx.x)	xx (xx.x)
Serious Adverse Events	xx (xx.x)	xx (xx.x)
Adverse Events Leading to Discontinuation of Investigational Product	xx (xx.x)	xx (xx.x)
Fatal Adverse Events	xx (xx.x)	xx (xx.x)

Table 2.1. - Table 2.15 (Open). Overview of Subject Incidence of Adverse Events (AEs)

Subject Incidence of AEs – Cohort 3 (810 mL)

Full Analysis Population – F1 (N=XX)

**FDP-1
 Phase I**

	Total (N=XX) n (% ^a)
Adverse Events	xx (xx.x)
Treatment Emergent Adverse Events	xx (xx.x)
Treatment-Emergent Adverse Events Related to Study Treatment	xx (xx.x)
Serious Adverse Events	xx (xx.x)
Adverse Events Leading to Discontinuation of Investigational Product	xx (xx.x)
Fatal Adverse Events	xx (xx.x)

Notes: Subjects may be counted in more than one row.

^a=Denominator for each % is the treatment group N.

Table 2.1. - Table 2.15 (Closed). Overview of Subject Incidence of Adverse Events (AEs)
Subject Incidence of AEs – Cohort 3 (810 mL)
Full Analysis Population – F1 (N=XX)
FDP-1
Phase I

	A (N=XX) n (% ^a)	B (N=XX) n (% ^a)
Adverse Events	xx (xx.x)	xx (xx.x)
Treatment Emergent Adverse Events	xx (xx.x)	xx (xx.x)
Treatment-Emergent Adverse Events Related to Study Treatment	xx (xx.x)	xx (xx.x)
Serious Adverse Events	xx (xx.x)	xx (xx.x)
Adverse Events Leading to Discontinuation of Investigational Product	xx (xx.x)	xx (xx.x)

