Subject ID	Sex/Age	Infusion Number [1]	Visit	Collection Date/Time	Vital Sign Test	Result	Unit
XXXXXX	X/XX	X	X	DDMMYY:TT	XXXXX	XXXXX	XXXXX
		X	X	DDMMYY:TT	XXXXX	XXXXX	XXXXX
		X	X	DDMMYY:TT	XXXXX	XXXXX	XXXXX
		X	X	DDMMYY:TT	XXXXX	XXXXX	XXXXX
XXXXXX	X/XX	X	X	DDMMYY:TT	XXXXX	XXXXX	XXXXX
		X	X	DDMMYY:TT	XXXXX	XXXXX	XXXXX
		X	X	DDMMYY:TT	XXXXX	XXXXX	XXXXX
		X	X	DDMMYY:TT	XXXXX	XXXXX	XXXXX

[1] Infusion Number: 1=Infusion #1; 2=Infusion #2.

Program Path:
Data source: ADVS

Data extract date:

Listing 13. Treatment-Emergent Adverse Events

Arm: XXXXXX

Subject ID	Sex/Age	Date of Enrollment	Randomization Date	Adverse Event Start Date	Body System or Organ Class	Preferred Term	Ongoing	Toxicity Grade [1]	Serious	Related to Study Drug [2]	Action Taken [3]	Outco [4]	
											Related to Study Drug [2]	Action Taken [3]	Outco [4]
XXXXXX	X/XX	DDMMYYYY	DDMMYYYY	DDMMYYYY	XXXXXXXXXXXX	XXXXXXXXXXXX	X	X	X	X	X	X	X
XXXXXX	X/XX	DDMMYYYY	DDMMYYYY	DDMMYYYY	XXXXXXXXXXXX	XXXXXXXXXXXX	X	X	X	X	X	X	X
XXXXXX	X/XX	DDMMYYYY	DDMMYYYY	DDMMYYYY	XXXXXXXXXXXX	XXXXXXXXXXXX	X	X	X	X	X	X	X
XXXXXX	X/XX	DDMMYYYY	DDMMYYYY	DDMMYYYY	XXXXXXXXXXXX	XXXXXXXXXXXX	X	X	X	X	X	X	X
XXXXXX	X/XX	DDMMYYYY	DDMMYYYY	DDMMYYYY	XXXXXXXXXXXX	XXXXXXXXXXXX	X	X	X	X	X	X	X

[1] Grade 1=Mild; 2=Moderate; 3=Severe; 4=Life-Threatening; 5=Fatal.

[2] Related to Study Drug: 1=Not Related; 2=Unlikely; 3=Possible; 4=Probable; 5=Definite.

[3] Action Taken: 1=Dose Increased; 2=Dose Not Changed; 3=Dose Reduced; 4=Drug Interrupted; 5=Drug Withdrawn; 6=Not Applicable; 7=Unknown.

[4] Outcome: 1=Recovered/Resolved; 2=Recovered/Resolved with Sequelae; 3=Recovering/Resolving; 4=Not Recovered/Not Resolved; 5=Fatal; 6=Unknown.

Listing 14. Listing of Unique Adverse Events

Arm: XXXXXXX

Body System or Organ Class	Preferred Term	Reported Term for the Adverse Event
XXXXXXXXXXXXXX	XXXXXXXXXXXX	XXXXXXXXXXXX

Note: Terms are sorted by reported term.

Program Path:
Data source: ADAE

Data extract date:

Listing 15. Treatment-Emergent Adverse Events at Least Probably Related to Study Drug

Arm: XXXXXXX

Subject ID	Sex/Age	Date of Enrollment	Randomization Date	Adverse Event Start Date	Body System or Organ Class	Preferred Term	Ongoing	Toxicity Grade [1]	Serious	Related to Study Drug [2]	Action Taken [3]	Outc [4]
XXXXXX	X/XX	DDMMYY	DDMMYY	DDMMYY	XXXXXXXXXXXX	XXXXXXXXXX	X	X	X	X	X	X
XXXXXX	X/XX	DDMMYY	DDMMYY	DDMMYY	XXXXXXXXXXXX	XXXXXXXXXX	X	X	X	X	X	X
XXXXXX	X/XX	DDMMYY	DDMMYY	DDMMYY	XXXXXXXXXXXX	XXXXXXXXXX	X	X	X	X	X	X

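### The headline related-TEAE row and Listing 15 leave out events rated possible, a narrower cut than stopping rule 1 and the SAE form use, and no reason is given

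*Protocol*

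**What the plan says.** Protocol 10.3 sets a five-level causality scale: not related, unlikely, possible, probable, definite. For possible, it says: "An association between the event and the administration of investigational product cannot be ruled out". Probable needs a high degree of certainty and an event that the subject's clinical state or other therapy cannot explain.

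For analysis, Protocol 11.1.3 and SAP 4.5.3 split the scale between possible and probable, in identical words: "TEAEs related to study treatment will be defined as definitely or probably related to study treatment". Two planned outputs use that split:

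- the row "Treatment-Emergent Adverse Events Related to Study Treatment" in SAP Tables 2.1-2.20;
- "Listing 15. Treatment-Emergent Adverse Events at Least Probably Related to Study Drug".

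The same sections also promise the full breakdown: "For all TEAEs, relatedness to infused product will be presented". SAP Tables 4.1-4.9 do this with one column per level.

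Other parts of the plan draw the line lower. Stopping rule 1 (Synopsis, Protocol 6.5 and 6.9.1, SAP 1.1) covers "An SAE that is determined to be possibly, probably, or definitely related to the study product". Stopping rule 3 reads "An AE related to the study product that requires medical or surgical intervention to prevent occurrence of an SAE", and it, like rule 2, names no level.

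**The concern.** Safety is the question this trial asks, and Protocol 11.1 lists FDP-related AEs among the things by which safety will be assessed. The related row of Table 2 is the one-line answer on that item. It uses a stricter cut than the rule that pauses the study, so a possibly related SAE could halt infusions while the related row for that arm reads 0%. Table 2 has no footnote stating its threshold, so a reader of the table alone cannot tell that possible events are excluded.

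The cross-dose view matters most in an ascending-dose study. Tables 4.1-4.9 are produced cohort by cohort and have no overall version. Tables 3.10-3.12, 7.1-7.3 and 8.1-8.3 put all doses on one page but carry no relatedness. The SUSAR tables (7.4-7.6) do span doses, but they cover only SUSARs and are left out of the DSMB reports. That leaves Tables 2.16-2.20 as the only planned summary of related events across doses.

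**Working it through.** **1. Where each document puts the cut**

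| Place | Levels treated as related |
|---|---|
| Protocol 11.1.3, SAP 4.5.3 | probable, definite |
| SAP Tables 2.1-2.20, related row | probable, definite (by that definition) |
| SAP Listing 15 | probable, definite (in its title) |
| Stopping rule 1 | possible, probable, definite |
| Protocol 10.2.5, unanticipated problems | related or possibly related (to participation) |
| Appendix A, Research Monitor reports | possible is enough for forwarding (relation to participation) |
| Appendix J, SAE form | not related and unlikely go to section 1; possible, probable and definite go to section 2 |
| Stopping rules 2 and 3 | related, no level given |

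The analysis definition is the outlier, and neither document gives a reason for it.

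**2. Where a possible event can still be seen**

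- Tables 4.1-4.9 have a separate possible column. The first row counts subjects, and each subject is counted once per row at the highest level of relatedness. Within an arm, possible + probable + definite in that row therefore gives the wider related count.
- Listings 13 and 18 carry the five-level code (3 = possible).
- A possibly related SAE after infusion appears in the TEAE and SAE rows of Table 2 and in Tables 7.1-7.3, which do not filter on relatedness.
- By SAP 4.5.3 the DSMB receives Tables 1.1-8.3 except 7.4-7.6, so Tables 4 and 7 reach it. That sentence names no listings.

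**3. The plan's own figure**

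The only precision figures are in Protocol Table 16 (SAP Table 3), which uses Clopper-Pearson intervals. With lower limit = Beta quantile(0.025; x, n − x + 1) and upper limit = Beta quantile(0.975; x + 1, n − x), n = 24 and x = 24 × 0.10 = 2.4 give 1.6% to 29.2%, width 27.6, as printed. The other eight cells also reproduce. The point here does not depend on that table, but the same formula is used below.

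**4. Size, in assumed cases**

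The documents contain no event counts. Assume one subject whose highest rating is possible, nobody with a probable or definite event, and the planned numbers (4 per arm, 8 per cohort, 24 in all). Rate = x/n.

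| Denominator | Current definition | Possible included |
|---|---|---|
| Arm, n = 4 | 0/4 = 0% (95% CI 0 to 60.2) | 1/4 = 25.0% (0.6 to 80.6) |
| Cohort, n = 8 | 0/8 = 0% (0 to 36.9) | 1/8 = 12.5% (0.3 to 52.7) |
| All, n = 24 | 0/24 = 0% (0 to 14.2) | 1/24 = 4.2% (0.1 to 21.1) |

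With two such subjects among 24 the rate is 2/24 = 8.3% (1.0 to 27.0), and with three it is 3/24 = 12.5% (2.7 to 32.4). The Table 2 shells have arm columns throughout and a cohort total only for Cohort 3 in the open session. The 24-subject line is therefore a pooled figure that a reader would compute, not a planned cell.

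**The case against.** The strongest reply is that nothing is lost. The cut is prespecified, worded identically in both documents, and printed in the title of Listing 15. All five levels are tabulated per arm, and the wider count needs only the addition of three cells in the first row of Table 4, which the DSMB receives. The primary endpoints are TEAEs, SAEs, SUSARs and deaths; the safety conclusion rests on TEAEs without a relatedness filter; and no hypothesis is tested. SUSARs come from reconciliation with the sponsor's SAE database, not from this flag. A precautionary pause rule also need not share its threshold with a descriptive summary.

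Most of this stands, and it rules out two stronger readings.

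- A reader might infer that possible events are counted as not related. They are not. Table 2 has no unrelated row, and Table 4 keeps possible apart from not related and unlikely.
- A reader might infer that most true reactions will be rated possible, so that the related rate is heavily biased downward. Section 10.3 does set a demanding standard for probable, but neither document gives any figure for how ratings will fall.

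The appeal to Protocol 10.2.1 is also weaker than it looks. "A suspected AR is any AE for which there is a reasonable possibility that the drug/biologic caused the AE" is explained there for IND safety reporting as needing evidence that suggests a causal relationship. That is not the same test as an association that cannot be ruled out.

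The reply does not explain the mismatch. It also does not supply a cross-dose related summary that includes possible events, or a threshold statement on Table 2.

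**Conclusion.** The point holds as an inconsistency in a reported safety summary. One descriptive row, in all of Tables 2.1-2.20, and one listing use a narrower meaning of related than stopping rule 1, the unanticipated-problem criteria and the SAE form, without explanation. The only planned cross-dose summary of related events inherits that gap. The primary safety counts are unaffected, and the omitted events can be recovered within each cohort.

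The actual effect cannot be known from the documents. The shift of 25, 12.5 or 4.2 percentage points per subject assumes that the subject has no probable or definite event and that the planned denominators hold without replacements or attrition. With arms of 4, one subject is enough to change the row visibly. Because full relatedness is shown elsewhere and no primary endpoint depends on the flag, the severity is below must-fix.

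A separate loose end is that stopping rules 2 and 3 use related with no level. It is unclear whether the analysis definition or the wording of rule 1 is meant to apply to them.

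**What to change.** - In Protocol 11.1.3 and SAP 4.5.3, define related TEAEs for analysis as possibly, probably or definitely related.
- Apply that to the related row of Tables 2.1-2.20, with a footnote stating the threshold.
- Keep the probable/definite count as a second row, so the stricter figure remains available.
- Widen Listing 15 to match and retitle it as at least possibly related.
- Reconcile stopping rules 2 and 3 with the analysis definition and with rule 1, so that each says which levels it covers. Which levels those should be is for the sponsor to state.

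The cost is one sentence in each document, one derived flag, one added row, a footnote and a listing title. The five-level rating is already collected, so no new data are needed. The drawback is that the reported related rate may look less favourable and will include some events that are not causal. Retaining the second row limits that.

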# 11.2. Planned Enrollment and Reason for Sample Size

The sample size for this single-site study is set to 24. The primary objective of this study is to assess the safety of single infusions with the RePlas FDP product at increasing fixed doses of either 1 unit (approximately 270 mL), 2 units (approximately 540 mL), or 3 units (approximately 810 mL) in normal healthy subjects. Safety will be measured using the following primary safety endpoints: AEs, TEAEs, SAEs, SUSARs, and deaths. The sample size was selected to reasonably balance the ability to address the study's primary objective while minimizing the number of subjects potentially at risk. Precision estimates were calculated using different safety outcome incidence rates and different sample sizes as exhibited in Table 16. For example, in 24 subjects, a safety outcome with an incidence rate of 10% would have a 95% confidence interval of 1.6-29.2% and a corresponding width=27.6 at a 2-sided alpha of 0.05. To account for subject attrition and for comparison purposes, a sample size of 20 and 28, are, respectively, included in Table 16.

Concurrent infusions will not take place across cohorts ensuring infusions at the next higher dose do not begin until all subject infusions at the previous dose have been completed. The duration for which each cohort will remain active has been estimated based on the study schedule such that Cohorts 1 and 2 are expected to each be active for approximately 6 months and Cohort 3 will be active for approximately 7 months.

Sections 5.10 and 7.1 contain information on the capabilities of HBC to recruit the required number of subjects for this study.

Table 16: Precision Estimates Based on Safety Outcome Incidence Rates and Sample Size

Sample Size		Incidence	
	10%	25%	50%
20	(1.2-31.7) δ=30.5	(8.7-49.1) δ=40.4	(27.2-72.8) δ=45.6
24	(1.6-29.2) δ=27.6	(9.8-46.7) δ=36.9	(29.1-70.9) $\delta$ =41.8
28	(2.0-27.3) δ=25.4	(10.7-44.9) δ=34.2	(30.6-69.4) δ=38.7

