4. STATISTICAL ANALYSIS CONSIDERATIONS

4.1 Sample Size and Power

The sample size for this single-site study is 24 subjects. Safety will be measured using the following primary safety endpoints: AEs, TEAEs, SAEs, SUSARs, and deaths. The selection of the sample size was based on reasonably balancing the ability to address the study's primary objective and to minimize the number of subjects potentially at risk. Different safety outcome incidence rates and sample sizes were used to calculate the precision estimates calculated and presented in Table 3; the accompanying confidence intervals are based on Clopper-Pearson and were calculated using PASS software Version 13.0.3.

As shown, a safety outcome occurring at a rate of 10% incidence in 24 subjects would have a 95% confidence interval from 1.6-29.2% and a corresponding width=27.6 at a 2-sided alpha of 0.05. To account for subject attrition and for comparison purposes, a sample size of 20 and 28, respectively, are included in the table.

Table 3. 95% Confidence Intervals and Precision (δ) for Incidence

Sample Size	Incidence		
	10%	25%	50%
20	(1.2-31.7) $\delta=30.5$	(8.7-49.1) $\delta=40.4$	(27.2-72.8) $\delta=45.6$
24	(1.6-29.2) $\delta=27.6$	(9.8-46.7) $\delta=36.9$	(29.1-70.9) $\delta=41.8$
28	(2.0-27.3) $\delta=25.4$	(10.7-44.9) $\delta=34.2$	(30.6-69.4) $\delta=38.7$

Concurrent infusions will not take place across cohorts to ensure infusions at the next higher dose do not begin until all subject infusions at the previous dose are completed. Based on the study schedule, the estimated duration for which each cohort will remain active is approximately 6 months for Cohorts 1 and 2, and for Cohort 3 approximately 7 months.

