4.5.3.1 Primary Safety Endpoints

The primary safety endpoints to be assessed are AEs, specifically:

- TEAEs;
- SAEs;
- SUSARs; and
- Deaths.

Descriptive statistics will be used to analyze the primary safety endpoints. Tables produced to exhibit the primary safety endpoint data will be presented by the specific type of plasma product infused. In Cohorts 1 and 2, this data will be presented by FDP product type, FDP-ACD and FDP-CPD; in Cohort 3 by experimental product and control product, FDP and FFP. The primary safety data reported to the DSMB for Cohort 3 will be masked. Unblinding during the study will only occur in accordance with Section 3.3.2 following Westat's SOP DA-504 Development of a Plan for Randomization, Masking, and Unmasking.

In general, AEs that occur in Cohort 3 subjects within 14 days after infusion will be attributed to the most recently infused product. However, there may be exceptions to use of this temporal attribution rule to all transfusion-related AEs given the possibility that those AEs that occur after infusion with the second product may potentially be related to infusion with the first infusion product (e.g., an immunogenic response).

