	Cohort 1		Cohort 2		Cohort 3
	FDP-CPD 270 mL (N = XX) n (% ^a)	FDP-ACD 270 mL (N = XX) n (% ^a)	FDP-CPD 540 mL (N = XX) n (% ^a)	FDP-ACD 540 mL (N = XX) n (% ^a)	810 mL (N = XX) n (% ^a)
Adverse Events	xx (xx.x)	xx (xx.x)	xx (xx.x)	xx (xx.x)	xx (xx.x)
Treatment Emergent Adverse Events	xx (xx.x)	xx (xx.x)	xx (xx.x)	xx (xx.x)	xx (xx.x)
Treatment-Emergent Adverse Events Related to Study Treatment	xx (xx.x)	xx (xx.x)	xx (xx.x)	xx (xx.x)	xx (xx.x)
Serious Adverse Events	xx (xx.x)	xx (xx.x)	xx (xx.x)	xx (xx.x)	xx (xx.x)
Adverse Events Leading to Discontinuation of Investigational Product	xx (xx.x)	xx (xx.x)	xx (xx.x)	xx (xx.x)	xx (xx.x)
Fatal Adverse Events	xx (xx.x)	xx (xx.x)	xx (xx.x)	xx (xx.x)	xx (xx.x)

Notes: Subjects may be counted in more than one row.

^a=Denominator for each % is the treatment group N.

Table 2.16. - Table 2.20 (Closed). Overview of Subject Incidence of AEs - Overall
Subject Incidence of AEs – Overall
Full Analysis Population – F1 (N=XX)
FDP-1
Phase I

	Cohort 1		Cohort 2		Cohort 3	
	FDP-CPD 270 mL (N = XX) n (% ^a)	FDP-ACD 270 mL (N = XX) n (% ^a)	FDP-CPD 540 mL (N = XX) n (% ^a)	FDP-ACD 540 mL (N = XX) n (% ^a)	A 810 mL (N = XX) n (% ^a)	B 810 mL (N = XX) n (% ^a)
Adverse Events	xx (xx.x)	xx (xx.x)	xx (xx.x)	xx (xx.x)	xx (xx.x)	xx (xx.x)
Treatment Emergent Adverse Events	xx (xx.x)	xx (xx.x)	xx (xx.x)	xx (xx.x)	xx (xx.x)	xx (xx.x)
Treatment-Emergent Adverse Events Related to Study Treatment	xx (xx.x)	xx (xx.x)	xx (xx.x)	xx (xx.x)	xx (xx.x)	xx (xx.x)
Serious Adverse Events	xx (xx.x)	xx (xx.x)	xx (xx.x)	xx (xx.x)	xx (xx.x)	xx (xx.x)
Adverse Events Leading to Discontinuation of Investigational Product	xx (xx.x)	xx (xx.x)	xx (xx.x)	xx (xx.x)	xx (xx.x)	xx (xx.x)
Fatal Adverse Events	xx (xx.x)	xx (xx.x)	xx (xx.x)	xx (xx.x)	xx (xx.x)	xx (xx.x)

Programming Note: The table will be repeated for all analysis populations that are determined to be on a different set of subjects as described in Section 4.2 (Table 2.17 – Table 2.20). All tables may not be produced based on the table reduction method mentioned in Section 4.2 and may not exactly match the SAP. The titles for the tables will be the same for the other populations with the name of the population changing based on the population being used.

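### The sample-size precision is stated only for about 24 pooled subjects, but every planned adverse-event table reports groups of 4 or 8, with no all-FDP column and no confidence interval

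*Protocol*

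**What the plan says.** Protocol 11.2 states that "The sample size for this single-site study is set to 24". It says this number balances the ability to meet the primary objective against exposing few people to risk, and then gives interval widths in Table 16. The worked example is that "in 24 subjects, a safety outcome with an incidence rate of 10% would have a 95% confidence interval of 1.6-29.2" per cent, with a "corresponding width=27.6 at a 2-sided alpha of 0.05". The other rows are explained thus: "To account for subject attrition and for comparison purposes, a sample size of 20 and 28". SAP 4.1 repeats the grid as Table 3 and adds that the "confidence intervals are based on Clopper-Pearson and were calculated using PASS software Version 13.0.3".

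For reporting, SAP 4.5.1 plans frequencies and percentages for categorical data, and SAP 4.5.3 summarises safety data by cohort. SAP 4.5.3.1 says: "Tables produced to exhibit the primary safety endpoint data will be presented by the specific type of plasma product infused". It and Protocol 11.1.1 then specify FDP-CPD and FDP-ACD in Cohorts 1 and 2, and FDP and FFP in Cohort 3.

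The AE shells in SAP section 5 (Tables 2.1 to 8.3) have one column per arm in Cohorts 1 and 2. Cohort 3 is a single total column (Open session) or two masked columns (Closed session), which are relabelled by treatment sequence in the final analysis. The footnote to the percentages reads "a=Denominator for each % is the treatment group N". Tables 2.16-2.20 and 3.10-3.12, although titled as overall summaries, set these columns side by side and do not pool them. A column across all cohorts exists only in Table 1.21 (populations and disposition) and Table 14 (exposure).

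**The concern.** The precision used to support the sample size belongs to a group that no planned AE output displays, and none is stated for the groups that are displayed.

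This bears on the primary objective, which is safety at three increasing doses, and on the DSMB's review after each cohort of 8. An entry of 0 (0.0) in a column of 4 would carry no sign of how high the true rate could still be. A reader who looks back to the sample-size section for guidance finds 1.6-29.2%, which does not describe that column.

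**Working it through.** **Inputs.** Total 24, incidences of 10%, 25% and 50%, two-sided alpha 0.05 (Protocol 11.2). Clopper-Pearson method (SAP 4.1). Four subjects per arm and 8 per cohort (SAP Table 1 and SAP 3.4). FDP-ACD recipients number 4 + 4 + 8 = 16. All FDP recipients number 8 + 8 + 8 = 24.

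**Formula.** With x = n × incidence, the lower limit is the 0.025 quantile of Beta(x, n − x + 1) and the upper limit is the 0.975 quantile of Beta(x + 1, n − x). With x = 0, the upper limit is 1 − 0.025^(1/n).

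**Reproducing the plan.** For n = 24 at 10%, x = 2.4, and the interval is 1.61% to 29.19%, width 27.58. The plan prints 1.6-29.2 and 27.6. The other eight cells of Table 16 also agree to rounding. Wilson (3.1-28.0%) and Wald (−2.0 to 22.0%) intervals do not match, which confirms the method the SAP names.

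**Same method at the group sizes concerned:**

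| n | Where it occurs | Width at 10% | Width at 25% | Width at 50% | Upper limit, 0 events |
|---|---|---|---|---|---|
| 24 | all FDP; no planned AE column | 27.6 | 36.9 | 41.8 | 14.2% |
| 16 | all FDP-ACD; no planned AE column | 34.4 | 45.1 | 50.7 | 20.6% |
| 8 | Cohort 3 total, or per product | 49.7 | 61.9 | 68.6 | 36.9% |
| 4 | each arm or sequence | 69.6 | 80.0 | 86.5 | 60.2% |

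**Ratios to the n = 24 widths.**
- n = 8: 49.7/27.6 = 1.8, 61.9/36.9 = 1.7, 68.6/41.8 = 1.6.
- n = 4: 69.6/27.6 = 2.5, 80.0/36.9 = 2.2, 86.5/41.8 = 2.1.

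The n = 4, 10% cell rests on 0.4 events, which cannot be observed. Results that can occur give the same message: 0 of 4 gives 0-60.2%, and 1 of 4 gives 0.6-80.6%.

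**Chance of at least one event when the true rate is 10%**, 1 − 0.9^n: 92.0% (n = 24), 57.0% (n = 8), 34.4% (n = 4).

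**Can n = 24 be recovered from the AE tables?** Not by adding columns. Each Cohort 3 subject receives both products, so the Cohort 3 columns mix events after FDP with events after FFP.

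**The case against.** The best defence is that nothing printed is wrong. The documents say what the interval would be in 24 subjects. They promise neither that precision at each dose nor a reported interval. The study is openly descriptive, the AE columns print their own N, and the layout of the overall AE tables matches that of the overall demographic tables. All of this stands. It does not remove the mismatch, because an interval is not a test, and the plan itself chose interval width to illustrate what its sample size gives.

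Three stronger readings are tempting, and the documents do not support them.
- A reader might infer that Table 16 is miscalculated. It reproduces in full.
- A reader might infer that the trial cannot deliver the stated precision. All 24 planned completers receive FDP, and Listings 13 and 18 show every treatment-emergent and serious event by subject. A pooled rate could therefore be derived using the 14-day attribution rule. What is missing is a planned output that does so.
- A reader might infer that precision is the only rationale for 24 subjects. Both documents first give the balance between meeting the objective and limiting exposure.

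Two further objections shape the fix. Pooling averages three doses and two anticoagulants, so it cannot replace the per-dose display. Also, the AE tables concerned go to the DSMB in Open and masked Closed form. A pooled FDP column there would need unmasked assignments, and subtracting the Cohort 1 and 2 columns would reveal the Cohort 3 FDP count.

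**Conclusion.** The point holds as a mismatch between the stated precision and the planned reporting. It is not an arithmetic error and gives no reason to change the sample size. No planned AE table shows the n = 24 precision, and none is given for the groups reported, where intervals are 1.6 to 1.8 times as wide (n = 8) or 2.1 to 2.5 times as wide (n = 4).

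The sizes 4, 8 and 24 are planned completers. Because discontinued subjects are replaced, columns for the wider populations could be slightly larger, which does not alter the conclusion. The group size in Cohort 3 is itself unsettled: the text of Protocol 11.1.1 and SAP 4.5.3.1 implies 8 per product, while the sequence-labelled shells imply 4 per column. Neither is 24.

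**What to change.** 1. In Protocol Table 16 and SAP Table 3, add rows for n = 4, 8 and 16, and give the upper 95% limit for zero events in each row. State that the n = 24 row applies only to all FDP recipients pooled across doses and anticoagulants.
2. In the final unblinded analysis only, and not in the DSMB Open or Closed tables, add an all-FDP column (planned n = 24) to Tables 2.16-2.20, 3.10-3.12 and 7.1-7.3. For Cohort 3, count only events attributed to the FDP infusion under the 14-day rule. Print exact Clopper-Pearson 95% intervals, and keep the per-dose columns as the primary display.
3. In the same final tables, present Cohort 3 by product, as Protocol 11.1.1 and SAP 4.5.3.1 already state.

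No extra subjects or data are needed. The cost is SAP wording, some programming, and a less favourable precision statement for each group. The attribution rule must also be applied event by event in Cohort 3. Because it allows exceptions without criteria, and does not say how to treat events more than 14 days after the second infusion, it should be made definite before unblinding.
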